4.1 Objectives and Endpoints

Ob	jectives	Endpoints						
Pr	imary							
•	To assess the safety and tolerability of multiple SC doses of AMG 598 administered alone or in combination with liraglutide in subjects with obesity	 Subject incidence of treatment-emergent AEs Safety laboratory data, vital signs, and ECGs 						
Se	condary							
•	To characterize the PK of multiple SC doses of AMG 598 administered alone or in combination with liraglutide in subjects with obesity	• AMG 598 PK parameters may include, but are not limited to, maximum observed concentration (Cmax), time of maximum observed concentration (tmax), and area under the concentration time curve (AUC)						
Ex	ploratory							
•	To characterize the PD effects of AMG 598	 PD parameters: Concentrations of fasting glucose, insulin, c-peptide, glucose dependent insulinotropic polypeptide (GIP), glucagon-like polypeptide type 1 (GLP-1), glucagon, and free fatty acid (FFA) Concentration-time profiles and AUC for metabolic parameters following a mixed meal tolerance test Lipid levels, including but not limited to, total cholesterol, low density lipoprotein cholesterol (LDL-C), high density lipoprotein cholesterol (HDL-C), and triglycerides Hemoglobin A1c (HbA1c) Potential biomarkers including, but not limited to, inflammatory and adipose tissue markers 						
•	To assess the effects of AMG 598 on body weight, waist circumference and BMI	 Change in body weight, waist circumference, and BMI 						
•	To assess the effect of AMG 598 on bone mineral density by dual energy x-ray absorptiometry (DXA) (cohorts 1-6)	 Changes in bone mineral density as measured by DXA (cohorts 1-6) 						
•	To assess the effect of AMG 598 on body composition (cohort 7)	 Changes in body composition as measured by whole body DXA (cohort 7) 						
•	To evaluate the immunogenicity of AMG 598	Incidence of anti-AMG 598 antibody formation						

4.2 Hypotheses

- AMG 598 will be safe and well tolerated following multiple SC dose administrations in subjects with obesity across the dose range evaluated
- AMG 598 in combination with liraglutide will be safe and well tolerated following multiple SC dose administrations in subjects with obesity across the dose range evaluated
- AMG 598 PK profile following multiple SC dose administrations will support selection of dose and frequency of administration in future multi-dose trials of AMG 598

5. Study Design

5.1 Overall Design

This is a randomized, placebo-controlled, double-blind, multiple ascending dose study in subjects with obesity. The study consists of 7 cohorts with SC administration of AMG 598 or matching placebo with and without liraglutide.

Approximately 108 subjects (8 per cohort for cohorts 1-6, 60 for cohort 7) will be enrolled. This study will be conducted at approximately 30 sites in the US.

For cohorts 1 to 6, eight subjects will be randomized to receive AMG 598 or placebo SC every 4 weeks (Q4W) x 3 in a 3:1 ratio at the proposed dose levels of 70, 210, and 420 mg on days 1, 29, and 57. All subjects in cohorts 1, 3, and 5 will undergo MMTT on day -1, 6 (+/- 1 day), and day 64 (+/- 1 day). Subjects in cohorts 2, 4, 6 and 7 will also receive liraglutide at up to 3.0 mg SC QD per the treatment schedule.

For cohort 7, sixty subjects that have been on a stable dose of liraglutide (3.0 mg SC QD) for at least 6 months will be randomized in a 1:1 ratio to receive AMG 598 or placebo. Subjects will continue to receive liraglutide (3.0 mg SC QD) and receive one dose of placebo on day -28, as part of a 4-week run-in. Subjects will then receive AMG 598 420 mg or placebo SC Q4W on days 1, 29, 57 in addition to stable liraglutide (3.0 mg SC QD).

Escalation to a higher dose cohort (cohorts 1 to 6) will only proceed when the previous dose regimen has been found to be safe and reasonably tolerated based on available safety and laboratory data through study day 36 for at least 6 out of 8 subjects dosed and upon unanimous recommendation at the DLRM. The planned dose escalation schedule may be modified based on treatment-emergent data (eg, safety and/or PK). Subsequent dosing will be guided by tolerability and safety. Dose adjustments for AMG 598, if any, will be made on a treatment cohort and not on an individual subject basis, and will be agreed upon by Amgen in conjunction with the Principal Investigator.

The overall study design is described by a study schema in Section 2.1. The endpoints are defined in Section 4.1.

5.2 Number of Subjects

Approximately 108 subjects will be enrolled in the study, with 8 subjects per cohort (cohort 1-6) and 60 subjects in cohort 7.

Subjects in this clinical investigation shall be referred to as "subjects". For the sample size justification, see Section 10.1.

5.2.1 Replacement of Subjects

Subjects who withdraw from the study or who discontinue study drug administration prematurely may be replaced at the discretion of Amgen in consultation with the investigator. The replacement subject will be assigned to receive the identical treatment as the replaced subject.

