- AMG 598 will be safe and well tolerated following multiple SC dose administrations in subjects with obesity across the dose range evaluated
- AMG 598 in combination with liraglutide will be safe and well tolerated following multiple SC dose administrations in subjects with obesity across the dose range evaluated
- AMG 598 PK profile following multiple SC dose administrations will support selection of dose and frequency of administration in future multi-dose trials of AMG 598

Overall Design

This is a randomized, placebo-controlled, double-blind, multiple ascending dose study in subjects with obesity. The study consists of a total of 7 cohorts; 3 cohorts (1, 3 and 5) with administration of AMG 598 or matching placebo SC every 4 weeks (Q4W) x3, 3 cohorts (2, 4 and 6) with Q4W x3 SC administration of AMG 598 or matching placebo in combination with liraglutide SC once daily (QD) ascending doses, and 1 cohort (cohort 7) with SC administration of AMG 598 or matching placebo SC Q4W x3 in addition to liraglutide (3.0 mg SC QD) in subjects who have been on a stable dose of liraglutide (3.0 mg SC QD) for at least 6 months or more. In cohorts 1-6, eight (8) subjects will be randomized to receive AMG 598 or placebo SC in a 3:1 ratio as described in the table below. In cohort 7, sixty (60) subjects will be randomized in a 1:1 ratio to receive AMG 598 or placebo SC as described in the table below.

Cohort	# Subjects	Product	Dose/ Frequency	Route	N (active: placebo)		
1	8	AMG 598/Placebo	70 mg Q4W x 3	SC	6:2		
2	8	AMG 598/Placebo	70 mg Q4W x 3 +	SC	6:2		
		Liraglutide	0.6, 1.2, 1.8, 2.4, 3.0 mg QD ^a	SC			
3	8	AMG 598/Placebo	210 mg Q4W x 3	SC	6:2		
4	8	AMG 598/Placebo	210 mg Q4W x 3	SC	6:2		
		+	+ 0.6, 1.2, 1.8, 2.4, 3.0 mg				
		Liraglutide	SC				
5	8	AMG 598/Placebo	420 mg Q4W x 3	SC	6:2		
6	8	AMG 598/Placebo +	420 mg Q4W x 3 +	SC	6:2		
		Liraglutide					
7	60	AMG 598/Placebo	420 mg Q4W x 3	SC	30:30		
		+ Liraglutide	+ 3.0 mg QD⁵				

Planned Dose Levels by Cohort

^a Subjects will start the first dose of liraglutide (0.6 mg, SC QD) on day 1, and increase the dose of liraglutide by 0.6 mg dose increment every 7 days, up to the full dosage of 3.0 mg by week 5 and remain on 3.0 mg until day 84, inclusive

^b Subjects eligible for the study will have been on a stable dose of liraglutide 3.0 mg SC QD for at least 6 months and will continue liraglutide 3.0 mg SC QD throughout the screening and study period from study days -56 to end of study (EOS) (day 207)

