7.2 Method of Treatment Assignment

On day -2 (cohorts 1, 3 and 5) or day -1 (cohorts 2, 4 and 6), or day 1 (cohort 7) eligible subjects will be randomized to a treatment assignment in a double-blind fashion. Within

each cohort, subjects will be randomly assigned in a 3:1 ratio (or 1:1 ratio in cohort 7) to receive either AMG 598 or placebo.

The randomization will be performed manually for cohorts 1-6 and, for cohort 7, by IVRS/IWRS. Subjects will be assigned a randomization number based in sequential order in which they qualified to be randomized. Subjects will be considered randomized once a unique subject randomization number has been assigned. Dosing should occur within 2 days of randomization for cohorts 1, 3 and 5, and 1 day of randomization for cohorts 2, 4, 6 and 7. The randomization date is to be documented in the subject's medical records and on the enrollment case report form (CRF).

A randomization schedule, based on a computer-generated randomization list prepared by Amgen, will be provided to the unblinded pharmacist at the site. The unblinded pharmacist will prepare all treatments accordingly and will randomize all subjects based on the randomization schedule.

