7.3.2 Access to Individual Subject Treatment Assignments by Amgen or Designees

Blinded individuals will not have access to unblinded information until the study is formally unblinded. Amgen staff and their designees involved in the study will not be blinded but will only be given treatment assignments when there is a need to use the information for analysis, discussion, and internal decision making. Access to treatment assignments and other restricted data are described in Amgen standard documents. Unblinded individuals are to ensure unblinding and potentially unblinding information

should not be distributed to the investigators or subjects prior to the study being formally unblinded.

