10.1 Sample Size Determination

The sample size for the study is based on practical considerations. For safety considerations, with up to 66 subjects receiving AMG 598 (6 subjects in each of cohorts 1-6 and 30 subjects in cohort 7), there is a 96.6% chance of detecting an adverse event with a true incidence rate of 5% or greater and a 99.9% chance of detecting an adverse event with a true incidence rate of 10%.

In cohort 7, with a sample size of 30 subjects per group, there is approximately an 80% probability of observing a mean treatment difference in percent change from baseline in body weight between AMG 598 and placebo of > 3%, assuming a true treatment difference of 5%. This assumes a standard deviation for percent change from baseline in body weight of 7% in each treatment group.

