3.2 Sample Size

Approximately 108 subjects (8 per cohort, cohorts 1-6; 60 in cohort 7) will be enrolled.

The sample size for the study is based on practical considerations. For safety considerations, with up to 66 subjects receiving AMG 598 (6 subjects in each of cohorts 1-6 and 30 subjects in cohort 7), there is a 96.6% chance of detecting an adverse event with a true incidence rate of 5% or greater and a 99.9% chance of detecting an adverse event with a true incidence rate of 10%.

In cohort 7, with a sample size of 30 subjects per group, there is approximately an 80% probability of observing a mean treatment difference in percent change from baseline in body weight between AMG 598 and placebo of > 3%, assuming a true treatment difference of 5%. This assumes a standard deviation for percent change from baseline in body weight of 7% in each treatment group.

Replacement of subjects:

Subjects who withdraw from the study or who discontinue study drug administration prematurely may be replaced at the discretion of Amgen in consultation with the investigator. The replacement subject will be assigned to receive the identical treatment as the replaced subject.

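### The same-treatment replacement rule does not exempt cohort 7, so subjects whose arm was not randomised can enter its 30:30 weight comparison; the likely bias is small and the fix is cheap

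*Protocol*

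**What the plan says.** - **Replacement.** Protocol 5.2.1 covers subjects who withdraw or stop study drug early. The replacement's arm is fixed: "The replacement subject will be assigned to receive the identical treatment as the replaced subject". SAP 3.2 repeats the rule directly after the cohort 7 sample-size paragraph; such subjects "may be replaced at the discretion of Amgen in consultation with the investigator". Neither section limits the rule to particular cohorts, sets a criterion for using it or caps the number.
- **Allocation.** The Protocol synopsis (Overall Design) states: "In cohort 7, sixty (60) subjects will be randomized in a 1:1 ratio to receive AMG 598 or placebo SC". Protocol 7.2 adds: "The randomization will be performed manually for cohorts 1-6 and, for cohort 7, by IVRS/IWRS". No section says how a same-treatment replacement would be issued through that system.
- **Before dosing.** Protocol 6.6 separately allows replacement of cohort 7 subjects who are terminated before receiving AMG 598/placebo. It does not switch off 5.2.1 for subjects who stop later.
- **Access to assignments.** Protocol 7.3.2 states: "Amgen staff and their designees involved in the study will not be blinded". The same sentence limits this: they receive assignments only when needed for analysis, discussion and internal decisions. Protocol 7.4.2.1 gives cohort 7 an unblinded medical monitor.
- **Analysis.** SAP 6.5 puts every dosed cohort 7 subject in the final analysis set, and Protocol 10.3.2.4.2 uses the safety set for exploratory endpoints. SAP 9.2 plans a listing of randomised and actual treatment. Neither document plans a flag for replacements or a weight summary without them.

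**The concern.** Same-treatment replacement serves a purpose in the 6:2 escalation cohorts, where losing one or two subjects would leave a dose level nearly empty. Cohort 7 has a different job. Protocol 3.1 gives it the preliminary look at weight loss, and its size rests partly on detecting a meaningful loss.

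In a 1:1 comparison, an arm assigned because someone else stopped is not a random assignment. The trigger comes after randomisation and may depend on treatment: Protocol 3.3.3.1 warns that the combination may cause more severe or longer gastrointestinal effects than liraglutide alone. The arm with more stopping would then receive more of the later, non-randomised entrants. Whether to replace is a discretionary choice with no stated criterion, and some of the sponsor's staff may know the assignments. The rule also links two subjects: if one is unblinded, anyone who knows the pairing knows the other's arm.

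At stake is how cleanly the cohort 7 weight difference can be read as a randomised comparison. The primary safety objective does not depend on it.

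**Working it through.** **Inputs from the plan (Protocol 10.1, SAP 3.2):** 30 per arm, true difference 5%, threshold 3%. "This assumes a standard deviation for percent change from baseline in body weight of 7% in each treatment group". **Assumed, because the documents give no rate:** the number of replacements, how far replacements differ from randomised subjects, and dropout.

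**1. The plan's own figure.** The plan says: "with a sample size of 30 subjects per group, there is approximately an 80% probability of observing a mean treatment difference" above 3%.
- SE = 7 × √(1/30 + 1/30) = 1.807.
- P(observed > 3) = Φ((5 − 3)/1.807) = Φ(1.107) = 86.6%, not 80%.
- The stated figure is close to two-sided 5% power against zero: Φ(5/1.807 − 1.96) = 79.0%. Both readings are carried below.

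**2. Who is in the set.** Dosed subjects who stop remain, so replacements add to the 30.

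| Replaced (active, placebo) | Dosed set | Non-randomised share, active | Non-randomised share, placebo |
|---|---|---|---|
| 3, 3 | 33:33 | 3/33 = 9.1% | 3/33 = 9.1% |
| 6, 2 | 36:32 | 6/36 = 16.7% | 2/32 = 6.3% |

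**3. Shift in the treatment difference.** If replacements differ from randomised subjects by b points in both arms, the shift is b × (active share − placebo share).
- 3 and 3 replaced: zero for any b.
- 6 and 2 replaced, all dosed subjects: b × (0.167 − 0.063) = b × 0.104, so 0.10 to 0.31 points for b = 1 to 3.
- 6 and 2 replaced, only the final 30:30 compared: b × (6/30 − 2/30) = b × 0.133, so 0.13 to 0.40 points.
- The largest of these, 0.40, is 0.40/1.807 = 0.22 of a standard error.

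**4. Cost of not replacing.**

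| Per arm | SE | P(observed > 3) | Two-sided 5% power |
|---|---|---|---|
| 30 | 1.807 | 86.6% | 79.0% |
| 27 | 1.905 | 85.3% | 74.7% |
| 24 | 2.021 | 83.9% | 69.7% |

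**5. Does replacement hide the subjects who stop?** Assume 20% of AMG 598 subjects stop and get no extra loss, while the rest lose 5 points more than placebo. The randomised difference is 0.8 × 5 = 4.0. Add six active replacements:
- If they stop at the same 20% rate, they average 4.0, and the arm gives (24×5 + 6×0 + 6×4)/36 = 4.0.
- If all six tolerate treatment: (24×5 + 6×0 + 6×5)/36 = 4.17.
- At 36 v 30, SE = 7 × √(1/36 + 1/30) = 1.730. P(observed > 3) is Φ(1.00/1.730) = 72% at 4.0 and Φ(1.17/1.730) = 75% at 4.17.
- If the stoppers' weights are missing and nobody is replaced, 24 v 30 already gives 5.0, with SE = 1.917 and Φ(2/1.917) = 85%.

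**The case against.** The best defence is that little depends on this. The study is phase 1b with a safety primary endpoint. Weight is exploratory, both documents mark the efficacy analysis as not applicable, and the 3% figure is a sample-size statement, not a decision rule. Replacement is optional, the plan expects little missing data, and discretion covers only whether to replace, since the arm then follows by rule. All of this stands and keeps the point small. It does not show that the rule fits cohort 7.

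Some stronger readings are tempting but not supported:

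- **Replacement refills the active arm with tolerators and inflates the effect**, for example from 4.0 to 5.0 points, taking the chance of exceeding 3% from 71% to 87% at 30 per arm. This needs the stoppers to drop out of the comparison. Under SAP 6.5 and Protocol 10.3.2.4.2 they stay in the set, and Protocol 8.1 asks that they remain on study. Step 5 shows no shift, or 0.17 points at most, when their weights are observed. If the weights are missing, the shift comes from not imputing them (Protocol 10.2.4, SAP 8.3). That is a separate issue, and it arises without any replacement.
- **Cohort 7 is the only controlled weight estimate.** Cohorts 1-6 also have randomised placebo subjects and scheduled weights.
- **Cohort 7 replacements are assigned by hand.** Manual randomisation is stated only for cohorts 1-6.
- **Unblinded staff decide who is replaced.** Access to assignments is on a need basis, and no section gives this decision to the unblinded medical monitor. Under Protocol 7.4.2.1 the safety surveillance team reviews blinded by default.

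**Conclusion.** The point holds as a low-severity design weakness. Followed as written, the plan permits subjects whose arm was set by another subject's discontinuation to enter a comparison that is otherwise randomised 1:1, and it plans nothing that would separate them in the weight results.

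The expected bias is about 0.1 to 0.4 percentage points in the unequal case examined, against an assumed true difference of 5. The upper end needs replacements that differ by 3 points and a comparison of only the final 30:30, which is not the planned set; in the planned set the top of the range is 0.31. Equal replacement with an equal shift gives no net bias, and if the option is never used after randomisation there is no effect. The case for changing the text rests on its low cost and on keeping the allocation clean, not on a large expected distortion.

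**What to change.** In Protocol 5.2.1 and SAP 3.2:

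- Limit the same-treatment rule to cohorts 1-6.
- For cohort 7, state that subjects are not replaced after randomisation, or that any added subject takes the next unused IVRS/IWRS number.
- State that every randomised and dosed cohort 7 subject stays in the assigned arm for the weight summary. The planned sets largely do this already; saying so prevents a summary of only the final 30:30.
- Leave replacement of run-in failures before randomisation as it is, since it does not affect allocation.

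This costs a sentence or two in each document. The downside is that the arms may end slightly below 30 or unequal. Dropout of 10% to 20% (assumed) leaves 27 to 24 per arm: about 85% to 84% on the criterion as worded, still above the stated 80%. If the 80% was meant as two-sided 5% power, the figures are about 75% to 70%. In that case, fresh randomisation of added subjects recovers the numbers while keeping allocation random.

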5.2.2 Number of Sites

Approximately 1-4 investigative sites in the United States will enroll into cohorts 1-6 and approximately 30 investigative sites in the United States will enroll into cohort 7.

5.3 End of Study

5.3.1 End of Study Definition

Primary Completion: The primary completion date is defined as the date when the last subject is assessed or receives an intervention for the final collection of data for the primary endpoint(s), for the purposes of conducting the primary analysis, whether the study concluded as planned in the protocol or was terminated early.

If the study concludes prior to the primary completion date originally planned in the protocol (ie, early termination of the study), then the primary completion will be the date when the last subject is assessed or receives an intervention for evaluation in the study (ie, last subject last visit).

End of Study: The end of study date is defined as the date when the last subject across all sites is assessed or receives an intervention for evaluation in the study (ie, last subject last visit), following any additional parts in the study (eg, long-term follow-up), as applicable.

5.3.2 Study Duration for Subjects

Cohorts 1 to 6

Subject participation will last up to approximately 235 days. This includes a 28-day screening period, a period of up to 2 days prior to investigational product (IP) administration and an on-study period lasting up to 207 days.

Cohort 7

Subject participation will last up to approximately 263 days. This includes a 28-day screening period, a 28-day run-in period, and an on-study period lasting up to 207 days.

5.4 Justification for Investigational Product Dose

The rationale for the dose selection and frequency (Q4W) in the current study is based on PK/PD analysis of animal data, as well as PK data from the ongoing FIH single ascending dose study of AMG 598 (20170138). In the FIH study, all 7 cohorts, totaling 56 subjects, have received a single dose of AMG 598 or placebo (AMG 598 dose ranges from 21 mg to 560 mg). Preliminary review of the PK data in the FIH single ascending dose study demonstrated linear PK and dose proportional C_{max} (AUC data pending), with a half-life of approximately 27 days (through 560 mg SC). The median peak serum concentrations after SC administration were observed in approximately 7 days. The anticipated exposure margins for the highest planned AMG 598 dose in the current study (420 mg SC Q4W) for C_{max} and AUC are 61 and 62, respectively calculated from the C_{max} and AUC at the NOAEL (200 mg/kg) of AMG 598 in combination with liraglutide in the 13-week toxicology study in monkeys (Table 5-1). The blinded safety data from the AMG 598 FIH single ascending dose study through day 15 of the 560 mg SC dose cohort supports the dose range to be evaluated in this study. In addition, a cohort where subjects received a single dose of AMG 598 560 mg SC in combination with liraglutide 0.6 mg SC QD for 7 days has completed dosing. Single ascending doses of AMG 598 have been safe and generally well tolerated. No SAEs or deaths have been reported, and most AEs reported were mild, with one moderate adverse event associated with gastroenteritis.

Based on the available PK and safety data from cohorts 1 to 6 reviewed at the DLRM #4 (Figure 2-1 Study Schema), the dose regimen for cohort 7 will be AMG 598 420 mg or placebo SC Q4W x 3. AMG 598 420 mg or placebo Q4W SC x 2 (safety data evaluated through study day 36) dosed concomitantly with liraglutide escalation was safe and generally well tolerated.

Table 5-1. Estimated Exposure Margins of AMG 598 for Multiple Doses (Q4W)

Estimated Exposure Margins of AMG 598 for Multiple Doses (NOAEL=200 mg/kg)								
Dose		Predicted AUC _{0-28day,last}	Predicted C _{max, last}	Expo Març				
Cohorts	(mg)	Route	(µg·day/mL)	(µg/mL)	AUC°	$C_{max}{}^{d}$		
1 and 2	70	SC	298	12.8	370	365		
3 and 4	210	SC	893	38.3	124	122		
5 and 6	420	SC	1790	76.6	62	61		

^a PK data (up to 280 mg cohort) from AMG 598 FIH study is used for PK prediction

^b Based on NOAEL of 200 mg/kg AMG 598 as a monotherapy or in combination with liraglutide in cynomolgus monkeys; AUC_{0-7day} (study days 85 to 92) = 27600 μg·day/mL (662000 hr*μg/mL divided by 24 hr/day) and C_{max} (study day 86) = 4670 μg/mL from 6 animals that were administered both 200 mg/kg AMG 598 SC weekly and 1.8 mg Liraglutide SC daily for 13 weeks.

^c AUC margin = [AUC_{0-7day,last dose}, cyno]×4/[AUC_{0-28day, last dose} human]

^d C_{max} margin = [C_{max,last dose}, cyno]/[C_{max,last dose} human]

